11.7 Where and how data or specimens will be stored?

Response: Consent forms and source data forms will be stored in locked files in the research office at UBMD Orthopaedics Location 2 at ECMC. The images will be saved on the PACS system at ECMC. Electronic data will be stored on our department's secure network drive in password protected files.

11.8 How long the data or specimens will be stored?

Response: The data will be stored throughout the duration of the study and final data analysis. The data will then be stored for 3 more years after the study closing date in accordance with the IRB policies.

11.9 Who will have access to the data or specimens?

Response: The study investigators, research coordinator and research assistant will have access to the data. Carestream Health, Inc. will also have access to the images upon request and under approval of the principal investigator. Images will be de-identified before sharing with Carestream Health, Inc.

11.10 Who is responsible for receipt or transmission of the data or specimens?

Response: The research coordinator or assistant is responsible for retrieving and storing the data.

11.11 How data and specimens will be transported?

Response: The research coordinator or assistant will pick up the study forms directly from the consenting and enrolling physicians after enrollment on a daily basis.

12.0 Provisions to Monitor the Data and Ensure the Safety of Subjects

12.1 Describe the plan to periodically evaluate the data collected regarding both harms and benefits to determine whether subjects remain safe.

Response: Adverse events will be reported to the Data Safety Monitoring Board (DSMB) within 2 days to review safety of the study.

12.2 Describe what data are reviewed, including safety data, untoward events, and efficacy data.

PROTOCOL TITLE: Comparison of a novel weight bearing cone beam computed tomography (CT) scan to gravity stress X-ray for determining instability of supination-external rotation type ankle fractures

Response: Any adverse events will be reported to the research coordinator and reviewed by the DSMB within 2 days of notification of the event.

12.3 Describe how the safety information will be collected (e.g., with case report forms, at study visits, by telephone calls with participants).

Response: Adverse events will be documented in writing during study visits.

12.4 Describe the frequency of data collection, including when safety data collection starts.

Response: Safety data collection will begin after signed informed consent is obtained and continues until all data has been collected from 20 patients.

12.5 Describe who will review the data.

Response: Data collection will be monitored by the University at Buffalo Clinical Research Office for appropriate reporting of all adverse events and any serious adverse events that may occur during the course of the trial. The PI will have oversight of all of the subject data.

12.6 Describe the frequency or periodicity of review of cumulative data.

Response: Given the small sample size and relative low risk of the study and procedures, cumulative data will be analyzed when 20 subjects have been enrolled.

12.7 Describe the statistical tests for analyzing the safety data to determine whether harm is occurring.

Response: Adverse events will be reviewed by the DSMB on a case-by-case basis to determine if harm is occurring.

12.8 Describe any conditions that trigger an immediate suspension of the research.

Response: This study is low risk and we are not aware of a specific condition that would suspend the study. The DSMB will review all adverse events and assist in determining if the study needs to be suspended.

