7.0 Study Timelines

7.1 *Describe the duration of an individual subject's participation in the study.*

PROTOCOL TITLE: Comparison of a novel weight bearing cone beam computed tomography (CT) scan to gravity stress X-ray for determining instability of supination-external rotation type ankle fractures

Response: The subject will be enrolled in the study once informed consent is obtained. The study will conclude once they have had a gravity stress X-ray as standard of care, and a CBCT scan with the investigational weight bearing cone beam scanner.

7.2 Describe the duration anticipated to enroll all study subjects.

Response: It is anticipated that it will take 8 months to 1 year (based on analysis of the past frequency of patients with the diagnosis of an unstable SER fracture and the difficult nature of enrolling study patients) to enroll all study subjects.

7.3 Describe the estimated date for the investigators to complete this study (complete primary analyses)

Response: The estimated date for the investigators to complete the primary analysis is the first quarter of 2017.

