8.0 Study Endpoints

8.1 Describe the primary and secondary study endpoints.

Response: The primary endpoint is after enrollment of 20 subjects estimated to provide significance by power analysis.

8.2 Describe any primary or secondary safety endpoints.

Response: The primary safety endpoint is the presence of any adverse event.

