28.2 Describe where the consent process take place

Response: Subjects will be consented in the ECMC emergency department or physician's offices.

28.3 Describe any waiting period available between informing the prospective subject and obtaining the consent.

Response: Subjects will be consented when they are initially diagnosed with a potentially unstable SER type ankle fracture and before they are sent for their gravity stress x-ray and investigational cone beam CT scan.

28.4 Describe any process to ensure ongoing consent.

Response: Subjects will be consented once at the beginning of the study. There is only one study visit so ongoing consent is not necessary.

28.5 Describe whether you will be following "SOP: Informed Consent Process for Research (HRP-090)." If not, describe:

- *The role of the individuals listed in the application as being involved in the consent process.*
- *The time that will be devoted to the consent discussion.*
- *Steps that will be taken to minimize the possibility of coercion or undue influence.*
- *Steps that will be taken to ensure the subjects' understanding.*

Response: Yes, HRP-090 will be followed when consenting.

Non-English Speaking Subjects

28.6 Indicate what language(s) other than English are likely to be spoken/understood by your prospective study population or their legally authorized representatives.

Response: Spanish is the most likely non-English language that we might encounter in this study population. Non-English speakers will be included in this study. Information for non-English speakers will be provided in oral form with the use of an interpreter.

PROTOCOL TITLE: Comparison of a novel weight bearing cone beam computed tomography (CT) scan to gravity stress X-ray for determining instability of supination-external rotation type ankle fractures

28.7 *If subjects who do not speak English will be enrolled, describe the process to ensure that the oral and written information provided to those subjects will be in that language. Indicate the language that will be used by those obtaining consent.*

Response: Based on previous experience, we expect that most if not all of our potential study subjects will speak English. However, if we encounter a non-English speaking subject we will find someone who can orally translate (i.e., fluently speaks the same language as the subject, such as a family member) the study description and consent form to the subject.

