Attachment D: Data Form

SER Ankle Fracture Instability STUDY: DEMOGRAPHIC DATA COLLECTION FORM

STUDY ID#: _____

TODAY'S DATE: _____

AGE: _____

GENDER (check one): _____ Male

_____ Female

RACE: _____

HEIGHT: _____

WEIGHT: _____

PATIENT'S DOCTOR: _____

AFFECTED SIDE: _____ Right

_____ Left

COURSE OF TREATMENT: _____

PROTOCOL TITLE: Comparison of a novel weight bearing cone beam computed tomography (CT) scan to gravity stress X-ray for determining instability of supination-external rotation type ankle fractures

SER Ankle Fracture Instability STUDY: CT DATA COLLECTION FORM

STUDY ID #: _____

DATE OF CT SCAN: _____

RADIOLOGIST: _____

RESULTS OF CT SCAN:

Date of Measurement: _____

Medial Clear Space Distance: _____

Superior Clear Space Distance: _____

Lateral Overlap Distance: _____

Lateral Clear Space Distance: _____

Lateral Talar Shift: _____

Total Weight Bearing: _____

Percent Weight Bearing: _____

PROTOCOL TITLE: Comparison of a novel weight bearing cone beam computed tomography (CT) scan to gravity stress X-ray for determining instability of supination-external rotation type ankle fractures

SER Ankle Fracture Instability STUDY: X-RAY DATA COLLECTION FORM

STUDY ID #: _____

DATE OF X-RAY: _____

RADIOLOGIST: _____

RESULTS OF X-RAY:

Date of Measurement: _____

Medial Clear Space Distance: _____

Superior Clear Space Distance: _____

Lateral Overlap Distance: _____

Lateral Clear Space Distance: _____

Lateral Talar Shift: _____

PROTOCOL TITLE: Comparison of a novel weight bearing cone beam computed tomography (CT) scan to gravity stress X-ray for determining instability of supination-external rotation type ankle fractures

Visual Analogue Scale

On a scale of 0 to 10, where 0 equals no pain and 10 equals extreme pain, please circle the number that best represents how much ankle pain you experienced during the scan.

| | | | | | | | | | |
0 1 2 3 4 5 6 7 8 9 10

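### No active adverse-event ascertainment is specified after the imaging visit, and patients who do not complete the scan leave the safety record, although the primary safety endpoint is any adverse event

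*Combined protocol and SAP*

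**What the plan says.** Section 8.2 states: "The primary safety endpoint is the presence of any adverse event". Section 12.3, whose prompt offers case report forms, study visits and telephone calls as examples of collection methods, is answered in one sentence: "Adverse events will be documented in writing during study visits". On timing, 12.4 says: "Safety data collection will begin after signed informed consent is obtained and continues until all data has been collected from 20 patients".

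The length of contact with a subject is set elsewhere. Section 28.4, on ongoing consent, says: "There is only one study visit so ongoing consent is not necessary". Section 7.1 says of each subject: "The study will conclude once they have had a gravity stress X-ray as standard of care, and a CBCT scan" on the investigational scanner.

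Under 12.1 and 12.2, events go to the research coordinator and are reviewed by the DSMB within 2 days of notification. Neither section says who would ask a patient about events once the visit is over. Section 13.3 keeps no data from a patient who does not complete the cone beam CT. Attachment D contains demographic, CT, X-ray and pain forms but no adverse-event form.

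The pain sheet is filled in after each of the two examinations (9.2). It asks the patient "how much ankle pain you experienced during the scan" and, as printed, has no field for study ID, date or examination.

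**The concern.** The study adds one physical exposure to routine care: standing on an ankle with a potentially unstable fracture during the scan. Section 9.2 names pain from weight bearing as a risk, and 9.3 describes measures against falling. The endpoint in 8.2 has no time limit, so a symptom that appears the next day counts as much as one during the scan. The stated method, however, has no planned look at the patient after the imaging is finished.

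Two things are at stake. A report of no adverse events could reflect a short observation window as much as safety, and the reader could not tell which. In addition, the DSMB reviews events case by case (12.7) and so depends entirely on what is brought to it. The rule in 13.3 adds to this, because a patient stopped during the scan for pain belongs to the group most relevant to the safety question, yet that patient's data are not kept.

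**Working it through.** The plan gives no event rate, target or precision for safety, so there is no figure of its own to reproduce here. The check is a comparison of sections, followed by two short calculations.

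**1. The sections side by side**

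- *What counts:* any adverse event (8.2).
- *When collection runs:* from consent until the data of 20 patients are complete (12.4). With 8 months to 1 year of enrolment (7.2), that is many months for the first patient and almost nothing for the last.
- *How events are collected:* in writing, at study visits (12.3).
- *How many visits:* one (28.4). The Screening/Enrollment Visit in 9.2 comes before loading, so it adds no later contact.
- *When participation ends:* after both examinations (7.1).
- *What remains after the visit:* a report to the coordinator (12.2), with no stated source or schedule.
- *Who is dropped:* anyone who does not complete the CT (13.3).

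Section 12.4 can be read in two ways. As a follow-up period for each patient, it has no method behind it and conflicts with 7.1 and 28.4. As the calendar period over which the study collects safety data, it does not conflict, but then no patient has any follow-up after imaging. On either reading no active ascertainment is specified.

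**2. What no events in 20 would show if every event were captured**

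The exact upper limit for 0/n is 1 − α^(1/n).

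- One-sided 95%: 1 − 0.05^(1/20) = 0.139.
- Upper end of the two-sided 95% interval: 1 − 0.025^(1/20) = 0.168.

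This limit comes from the sample size, not from the capture method.

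**3. How incomplete capture changes the chance of an empty record**

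Let r be the true event rate and f the share of events that surface after the visit and are not captured. Both are assumptions; neither is in the documents. Then

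P(no event recorded in 20) = (1 − r(1 − f))^20.

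At r = 10%: f = 0 gives 0.90^20 = 0.122; f = 25% gives 0.925^20 = 0.210; f = 50% gives 0.95^20 = 0.358; f = 90% gives 0.99^20 = 0.818.

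The same formula over a range of rates:

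| Assumed rate r | f = 0 | f = 25% | f = 50% | f = 90% |
|---|---|---|---|---|
| 2% | 67% | 74% | 82% | 96% |
| 5% | 36% | 47% | 60% | 90% |
| 10% | 12% | 21% | 36% | 82% |
| 20% | 1% | 4% | 12% | 67% |

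At low rates an empty record is likely whatever the method, so sample size dominates. At 10% to 20% the capture method makes most of the difference.

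**The case against.** The strongest case on the other side has five parts.

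- **The text does not restrict collection to the visit.** Section 12.3 does not say that events are recorded nowhere else. Section 12.2 covers any adverse event without tying it to a visit, and 12.5 has the university's clinical research office monitor reporting during the trial. This stands. A reader might infer that later harm cannot be captured at all, and the documents do not support that: acute events can be written down at the visit, and later ones may still reach the coordinator. What is missing is a planned step that looks for them.
- **There may be a later contact.** The CT and X-ray may be up to 7 days apart in either order (9.2). If the X-ray comes second, the patient is seen again after loading and completes a pain sheet. This stands for those patients, but the order is not fixed, and 28.4 counts one visit.
- **The named risks are immediate.** Pain and falling during a scan of about 25 seconds would be evident at once. This also stands. A reader might infer that the protocol recognises delayed harm from loading, and it does not. The point rests on the unrestricted endpoint in 8.2, not on evidence that such harm occurs.
- **The rates are invented and no safety rate is a planned estimate.** The table is illustrative and should not be read as an estimate of missed events. The mismatch between sections does not depend on it.
- **The pain sheet is a clerical matter.** Subjects have ID numbers (11.3), data are fully verified (11.4) and the coordinator collects the forms (11.5). A reader might infer that the pain data will be unusable. Staff would probably label the sheets by hand, so that inference goes too far.

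On 13.3, a reader might also infer that an event in a non-completer would never be reported. Sections 12.1 and 12.2 would still send it to the DSMB. What 13.3 removes is that patient's retained data, and so the patient's place in the final safety record.

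**Conclusion.** The point holds in this limited form. Followed as written, the plan elicits no adverse events after a subject's imaging is complete, and later events enter only by passive report. Sections 7.1, 12.3, 12.4 and 28.4 need to be reconciled with one another and with the endpoint in 8.2. Section 13.3 separately conflicts with an endpoint of any adverse event, because it removes non-completers, among them those who tolerated loading worst.

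The size is not known from the documents: the 12% to 82% span at a 10% rate rests wholly on the assumed rate and late share. The 13.9% limit needs only 20 subjects and full capture, and shows that an empty record would be weak evidence of safety even then. The comparison of medial clear space is unaffected. The change is worth making because it is cheap, but the point does not threaten the study's main result.

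**What to change.** 1. Change 12.3 to read: *at the study visit and by medical-record review through each subject's next routine visit for this injury*, with a latest date stated in the protocol so that the window closes for every subject.
2. Align 7.1 and 12.4 with that window, defined per subject, so that record review does not run past the stated end of participation. Check that the authorization mentioned in 25.1 covers it.
3. Limit 13.3 so that adverse-event data are kept for every subject in whom the scan was started, whether or not it was completed.
4. Report adverse events among all those subjects with an exact 95% confidence interval. The denominator may exceed 20, since 23.2 asks for 20 who complete the procedures.
5. As a minor form edit, add study ID, date and a CT / X-ray box to the pain sheet. A paired comparison of the two pain scores would then be possible, but is optional.

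Subjects are already under the care of the study investigators (22.2), and the team has access to their medical records (25.3). The cost is therefore a short chart review by the coordinator for about 20 patients and a few edits to text and form, with no added visit or test.

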13.0 Withdrawal of Subjects

13.1 Describe anticipated circumstances under which subjects will be withdrawn from the research without their consent.

Response: If the patient is noncompliant or unable to stand in the weight bearing position, they will be withdrawn. If the subject exhibits any discomfort the study will be stopped immediately.

13.2 Describe any procedures for orderly termination.

PROTOCOL TITLE: Comparison of a novel weight bearing cone beam computed tomography (CT) scan to gravity stress X-ray for determining instability of supination-external rotation type ankle fractures

Response: Subjects will be withdrawn from the study by the principal investigator if they do not complete the investigational CBCT scan. Subjects can withdraw from the study at any time, for any reason.

13.3 Describe procedures that will be followed when subjects withdraw from the research, including partial withdrawal from procedures with continued data collection.

Response: If the patient does not complete the investigational cone beam CT scan, none of their data will be retained.

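### Section 13.3 discards all data from subjects who do not complete the CBCT, with no exception for adverse events, against the any-adverse-event safety endpoint in 8.2

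*Combined protocol and SAP*

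**What the plan says.** Section 13.2 has the principal investigator withdraw any subject who does not complete the investigational scan. Section 13.3 then says: "If the patient does not complete the investigational cone beam CT scan, none of their data will be retained".

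The safety provisions are elsewhere:

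- **8.2:** "The primary safety endpoint is the presence of any adverse event".
- **12.4:** "Safety data collection will begin after signed informed consent is obtained and continues until all data has been collected from 20 patients".
- **12.2:** "Any adverse events will be reported to the research coordinator and reviewed by the DSMB within 2 days of notification of the event".
- **12.3:** "Adverse events will be documented in writing during study visits".
- **12.5:** the university's research office monitors data collection "for appropriate reporting of all adverse events and any serious adverse events that may occur during the course of the trial".
- **12.6:** "cumulative data will be analyzed when 20 subjects have been enrolled".
- **12.7:** "Adverse events will be reviewed by the DSMB on a case-by-case basis to determine if harm is occurring".

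Section 9.2 names pain from loading the injured ankle as a risk of the scan. It provides for stopping on undue discomfort, with exclusion if the scan cannot be done. Section 13.1 sets a lower threshold and stops for any discomfort. Section 9.2 also asks for a pain VAS after each imaging procedure, and 11.6 lists that score among the data collected.

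**The concern.** The rule in 13.3 depends on the outcome of the study procedure. A subject stopped because standing on the fractured ankle hurt is withdrawn under 13.2 and, under 13.3, leaves nothing in the retained data. That subject may have experienced the foreseeable harm of the device. The retained adverse-event and CBCT pain data would then describe completers only, and could look more favourable than the experience of everyone who attempted the scan.

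The safety endpoint asks whether any adverse event is present, so a single omitted event can change the answer. Staff also cannot follow 13.3 literally and still keep a full safety record from consent onward.

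**Working it through.** **1. The provisions side by side.**

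| Question | Section 12 and 8.2 | Section 13.3 |
|---|---|---|
| Who is covered? | Everyone from signed consent (12.4) | Those who do not complete the CBCT |
| Does completion matter? | No such condition | It decides whether anything is kept |
| Are adverse events included? | Yes; 12.4 calls them safety data | No exception to the rule that nothing is kept |
| Are records of withdrawn subjects kept? | Not stated | No |

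Section 12 governs recording, reporting and review. It does not say that a withdrawn subject's records are kept. The Attachment D forms, as shown, have no field for an incomplete scan, the reason for it, or an adverse event.

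**2. The plan's own figure.** Section 11.2 gives 80% power for 20 patients, SD of the difference 1.5 mm, difference 1 mm, alpha 0.05. A two-sided paired t-test has noncentrality 1/(1.5/√20) = 2.98 on 19 df and power 80.7%, so the figure reproduces. Section 23.2 counts 20 subjects who complete, so neither 13.3 nor its correction changes this.

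**3. How often the rule might apply.** The documents give no non-completion rate, so p per attempt is an assumption. Attempts are taken as independent, with non-completers replaced until 20 complete (23.2).

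- Chance of at least one non-completer = 1 − (1 − p)^20
- Expected number of non-completers = 20p/(1 − p)

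| Assumed p | Chance of at least one | Expected number |
|---|---|---|
| 1% | 1 − 0.99^20 = 18% | 0.2 |
| 2% | 1 − 0.98^20 = 33% | 0.4 |
| 5% | 1 − 0.95^20 = 64% | 1.1 |
| 10% | 1 − 0.90^20 = 88% | 2.2 |

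These count non-completion for any reason. For each p they are a ceiling on the chance of losing an adverse event from an attempted scan, because the stopped subject must also have had one.

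**4. What one omission does.** Exact (Clopper-Pearson) 95% intervals:

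| Case | Retained data | All attempts |
|---|---|---|
| The only adverse event is in one stopped subject | 0/20 = 0% (0 to 16.8%) | 1/21 = 4.8% (0.1 to 23.8%) |
| The one stopped subject had no adverse event | 0/20 = 0% (0 to 16.8%) | 0/21 = 0% (0 to 16.1%) |

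In the first case the answer to 8.2 changes from present to absent. In the second there is no favourable distortion. The intervals overlap heavily, so the loss is a missing event and not a demonstrable difference in rates.

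**The case against.** The best counter-argument is that 13.3 was never meant to reach adverse events. Sections 9.6 and 11.6 list the study data (demographics, imaging measures and pain VAS, plus weight borne in 9.6 and medical history in 11.6), and neither list names adverse events. Section 12 treats those separately, with their own start point, written record, monitor and reviewer, and 12.8 has the DSMB review all of them. On that reading 13.3 clears the research dataset, and the DSMB already knows whether any event occurred. The missing field in Attachment D affects completers too, so it is not caused by 13.3. No adverse-event rate or VAS analysis is planned, and the 18% to 88% figures are not the chance of losing an event.

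Much of this stands. Real-time review is intact, no planned test is biased, and the form gap alone proves nothing about 13.3. The number affected may also be small: people unable to stand are excluded at screening (3.1; Attachment A, item 11), the scan takes about 25 seconds (9.3), comfort supports can be added (20.5), and some subjects will fail to complete for other reasons, such as noncompliance (13.1). Completers can report pain as well.

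The separate-records reading is nevertheless an inference. Section 12.4 itself calls this information data, and no sentence exempts it from 13.3. Even on the narrow reading, the VAS is on the 11.6 list, so a stopped subject's pain score is discarded.

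**Conclusion.** The concern holds and should be fixed. Followed as written, 13.3 leaves adverse events and pain scores of non-completers out of the retained data and out of the cumulative analysis in 12.6, although 8.2 and 12.4 call for safety information on everyone from consent.

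The harm is an incomplete safety record. DSMB review as events occur, the paired t-test, the ROC analysis and the power are untouched. The size cannot be fixed from the documents: they give no stop rate and no rule on whether scan pain counts as an adverse event. The numerical illustrations rest on assumed non-completion rates and a scenario with one event. If the sponsor always intended to keep adverse events, the point reduces to stating that intent and keeping the pain scores.

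**What to change.** Replace 13.3 with wording such as:

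*Adverse events are retained for every consented subject. For a subject who attempts but does not complete the CBCT, the reason for stopping and any VAS already obtained are also retained, unless the subject withdraws permission.*

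Add one line to the CT form in Attachment D for scan not completed, reason, and adverse event. Report adverse events and available pain scores for all who attempted the scan, with the number and reasons for non-completion. Keep the paired t-test and the ROC analysis on completed pairs.

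The cost is one reworded section, one form line and a slightly fuller safety report. There is no added procedure, visit or patient. The safety figures may look less favourable. The consent pages are not in the reviewed text, so whether their wording on withdrawal must also change could not be checked.

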Study Visit: The subject will undergo a weight bearing CBCT scan of their affected ankle with the investigational portable cone beam CT scanner. This will be done at the same time or within 7 days as the gravity stress X-ray that is part of the routine clinical work-up for this injury. The scan with the investigational CBCT scanner is estimated to last approximately 25 seconds. The patient will be weight-bearing during the scan and can hold on to the built-in handles of the scanner for stability during the scan. The subject will be shielded from radiation to the thyroid and genitals with commercially available shields. The risks involved with this study include the risk of additional exposure to radiation delivered by the investigational CT scan. The investigational CBCT scanner exposes the patient to approximately 50% less radiation per scan than a conventional CT scanner. (Carrino et al 2014) With the investigational CBCT scan, there is the risk of pain caused by the need for weight bearing and/or flexion of an injured ankle. If for any reason the subject experiences undue discomfort the study will be stopped and the patient will be excluded from the study if the scan cannot be performed.

The patient will also fill out a visual analogue pain scale after both the investigational CT scan and gravity stress X-ray (**Attachment D**).

Reference: Carrino, J.A., et al., Dedicated cone-beam CT system for extremity imaging. *Radiology*, 2014. 270(3): p. 816-824.

9.3 Describe procedures performed to lessen the probability or magnitude of risks.

Response: The risks involved in inclusion in the study include the risk of additional exposure to radiation from the investigational CT scan. The investigational cone beam CT scanner exposes the patient to approximately 50% less radiation per scan than a conventional CT scanner. (Carrino et al 2014) The investigational scanner will be shielded per manufacturer specifications (see attachment B). The subject will be

PROTOCOL TITLE: Comparison of a novel weight bearing cone beam computed tomography (CT) scan to gravity stress X-ray for determining instability of supination-external rotation type ankle fractures

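### Section 13.3 keeps no data, safety data included, from subjects who do not complete the weight-bearing scan, so the reported safety results would cover only those who tolerated it

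*Combined protocol and SAP*

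**What the plan says.** All references are to the combined protocol and SAP.

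- **Retention.** Section 13.2: "Subjects will be withdrawn from the study by the principal investigator if they do not complete the investigational CBCT scan". Section 13.3 then says: "If the patient does not complete the investigational cone beam CT scan, none of their data will be retained". Neither makes an exception for any type of data, and no other section restores one.
- **Safety endpoint.** Section 8.2: "The primary safety endpoint is the presence of any adverse event". It is not limited to subjects who complete the scan.
- **Safety collection and review.** Section 12.4: "Safety data collection will begin after signed informed consent is obtained and continues until all data has been collected from 20 patients". Section 12.1: "Adverse events will be reported to the Data Safety Monitoring Board (DSMB) within 2 days to review safety of the study". Sections 12.2 and 12.3 add that events are written down at study visits and pass through the research coordinator. Section 12.7 has the DSMB judge harm case by case. Section 12.6 says that "cumulative data will be analyzed when 20 subjects have been enrolled".
- **Pain.** Section 9.2 names pain from loading the injured ankle as a risk of the scan. It also has the patient complete a visual analogue scale (VAS) for pain after the CT scan and after the gravity stress X-ray.
- **When to stop.** Section 13.1: "If the subject exhibits any discomfort the study will be stopped immediately". Section 9.2 says that if a subject "experiences undue discomfort the study will be stopped and the patient will be excluded from the study if the scan cannot be performed". Section 25.2 stops the study if the patient is physically or emotionally uncomfortable, whatever the reason. Section 20.5 provides padding, supports and other changes for comfort, and withdraws only those who cannot complete the scan.

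**The concern.** The subjects whom section 13.3 removes are not a random subset. Discomfort is the stopping trigger in sections 9.2, 13.1 and 25.2, and weight-bearing pain is the harm that section 9.2 foresees. The rule therefore takes out those most likely to have experienced it.

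At stake is the tolerability picture for an investigational device used on people standing on a fractured ankle. If the rule is followed to the letter, the data available for the cumulative analysis, and for any later report of adverse events, come only from completers. Any resulting bias makes the scanner look better tolerated than it was. How many subjects could not finish is itself a useful result, and no planned output gives it: the CT form in Attachment D has no field for a stopped scan or its reason. Data that are not retained cannot be recovered at the writing-up stage.

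**Working it through.** **1. The plan's own figure, and why it is not in question.** Section 11.2 gives n = 20, SD of the paired difference 1.5 mm, difference 1 mm, significance level 0.05 and power 80%. Taking the test as two-sided (sidedness is not stated), the noncentrality is (1/1.5) × √20 = 2.98 on 19 degrees of freedom. The noncentral t distribution then gives 80.7%, so the stated power reproduces. A subject without a completed CT scan has no paired difference. Keeping or discarding that subject's safety data therefore changes neither the paired t-test nor its power.

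**2. One stopped subject traced through the text.**

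- The subject consents, so safety collection has begun (12.4).
- The scan is started and stopped for pain (9.2 or 13.1).
- If this is recorded as an adverse event, it is written down and reviewed by the DSMB within 2 days (12.1 to 12.3).
- The principal investigator withdraws the subject (13.2).
- None of the subject's data are retained (13.3).
- At the cumulative analysis (12.6) and in any report against the 8.2 endpoint, the event and any pain score already given are absent.

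The Attachment A eligibility form is completed for every patient screened and records whether the patient enrolled. With the consent forms, it would allow a partial count of non-completers, but not the reasons.

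**3. Size.** No stop rate is given, so the counts below are assumptions that show scale and are not a forecast. Section 23.1 can be read as 20 enrolled in total (all assumed to start the scan). Section 23.2 reads as 20 who complete. With k stopped, the proportion is k/20 on the first reading and k/(20 + k) on the second. Intervals are exact (Clopper-Pearson) 95%.

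| Stopped (assumed) | 20 started in total | 20 completers |
|---|---|---|
| 0 | 0/20 = 0% (upper limit 16.8%) | same |
| 1 | 1/20 = 5.0% (0.1 to 24.9%) | 1/21 = 4.8% (0.1 to 23.8%) |
| 3 | 3/20 = 15.0% (3.2 to 37.9%) | 3/23 = 13.0% (2.8 to 33.6%) |
| 5 | 5/20 = 25.0% (8.7 to 49.1%) | 5/25 = 20.0% (6.8 to 40.7%) |

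The upper limit for no stops is 1 − 0.025^(1/20) = 16.8%. Each stop is worth about 5 percentage points. With no stops, section 13.3 removes nothing.

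**4. Stopping thresholds side by side.** Sections 13.1 and 25.2 stop at any discomfort; section 9.2 stops only at undue discomfort. Section 13.2, like 9.2 and 20.5, ties withdrawal to a scan that is not completed. Staff thus have two triggers, and the lower one leads more subjects into section 13.3. It is also unclear whether stopping the study means ending the scan or ending participation.

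**The case against.** The strongest case against the point is that section 13.3 was probably meant for the imaging measurements. It answers a prompt about withdrawal, whereas section 12 governs safety for every consented subject. Section 12.4 concerns collection and 13.3 retention, so the two need not collide. Section 12.5 adds outside monitoring of adverse event reporting. Patients who cannot stand are excluded at screening, and the scan lasts about 25 seconds, so stops may be few.

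Much of this stands. The imaging-only reading is plausible, but section 13.3 does not limit itself to imaging, and if that was the intent the amendment only states it. Screening and the short scan reduce the number of stops, yet sections 9.2, 13.1, 13.2 and 20.5 all still provide for scans that cannot be completed.

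A reader might also infer more than the documents support:

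- *That adverse events in stopped subjects escape safety review.* They do not; sections 12.1 to 12.3 apply to them in full.
- *That a planned adverse event rate would be driven to zero.* The plan specifies no such rate. Section 12.7 is case-by-case review, section 12.6 names no safety statistic, and a fall to zero would need every stop to carry an event and no completer to have one.
- *That a planned pain analysis is biased.* Section 11.1 plans no VAS analysis, and no section requires a CT pain score after an aborted scan. The loss applies only to scores actually obtained.
- *That the higher stopping threshold is the right one.* The lower one is more protective of people standing on a fracture, and choosing between them is a trade-off.

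**Conclusion.** The point holds as a stated retention rule with no safety exception. It should be corrected, ideally before the first scan is stopped. Followed literally, it confines the cumulative and reported safety results to subjects who tolerated the scan, and leaves the number stopped for pain unreported. The direction of any bias favours the device, on the reasoning that discomfort is the stated reason for stopping.

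The size cannot be determined from the documents: none if nobody stops, and about 5 percentage points of 20 subjects for each stop. DSMB review during the study and the medial clear space comparison are unaffected. The mismatch in stopping thresholds is real but is a minor matter of wording.

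**What to change.** 1. **Amend section 13.3.** For every consented subject who starts but does not complete the scan, and subject to that person's permission, keep four items: the fact of stopping, the reason, any adverse event, and any pain VAS score obtained. Include them in the safety results. Imaging measurements from non-completers can stay excluded.
2. **Add one field to the CT form in Attachment D:** completed, or stopped with reason. Report the number stopped out of the number started, with an exact 95% confidence interval.
3. **Minor clarification.** Use one stopping threshold in sections 9.2, 13.1 and 25.2, consistent with the comfort measures in section 20.5, and say whether stopping refers to the scan or to participation. Which threshold to use is for the investigator to choose.

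The cost is a few sentences of protocol text, one form field, and matching consent language with IRB approval. No procedure or radiation dose is added, and the sample size does not change.
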